169 Upon arrival to hotel, participants will be connected to a Tandem research pump connected to
170 the UVa DiAs platform and their Dexcom G6 Transmitter will be linked with DiAs. Participants will
171 then be taught how to use DiAs in this configuration. The research pump will be programmed
172 with the adolescent's usual insulin parameters.

173 Participants will have their blood sugar managed through this system during the entirety of the
174 time at hotel.

175 **1.3.5 Study Dinner Sessions**

176 *Study dinners and timing:* On four separate days (hotel days 2, 3, 6 and 7), participants will be
177 followed for the experimental dinners as part of the Study Dinner Sessions to compare blood
178 glucose control using four different approaches to insulin management for carbohydrate control
179 (Figure 1). These Study Dinner Sessions start approximately 3-4 hours before the dinner and
180 continue for approximately 12 hours after the dinner. During the Study Dinner Sessions,
181 participants will consume structured dinners (with identical protein, fat, and carbohydrate
182 content between the Study Dinner Sessions) while on the two UVa AP closed loop algorithms
183 (RocketAP or Control-IQ—in random order); for each, insulin dosing on the first Study Dinner
184 Session will be via normal carbohydrate announcement and the DiAs CGM-based bolus
185 calculator, and on the second Study Dinner Session with no carbohydrate announcement (In the
186 case of the RocketAP artificial pancreas system, the insulin priming will be in place to detect and
187 dose for unannounced carbohydrate.) For other meals on the artificial pancreas system during
188 the hotel stay, normal carbohydrate announcement will be performed.

CLINICAL PROTOCOL

189

Figure 1: Timeline of the Study Dinner Sessions

191 The order of the AP system tested (RocketAP vs. Control-IQ) is determined randomly. The order
192 of carbohydrate (CHO) announcement will be the same in both cases. Study Dinner Sessions will
193 likely be performed during two hotel admissions separated by no more than 8 weeks.

194 Blood glucose levels will be followed via continuous glucose monitor, and the primary outcome
195 will be percent time in blood glucose range 70-180 mg/dL during the 6 hours following start of
196 the meal. Study staff who will be present will include nursing staff and technical staff; a study
197 physician will be available either on-site or nearby off-site at all times. Hyperglycemia and

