198 hypoglycemia treatment protocols will be followed per CDT protocol. We anticipate more
199 significant cases of hyperglycemia during dinners managed without carbohydrate
200 announcement; participants will be encouraged to drink large amounts of non-caloric beverages,
201 particularly after these meals.

202 The UVa AP systems will be initiated upon arrival to the hotel the afternoon/evening before the
203 first of the Study Dinner Sessions. UVa CDT study staff will monitor CGM output continuously and
204 manage blood sugar control issues. At the end of the second Study Dinner Session, the
205 participant will be placed on home insulin management (or adjustment based on diabetes camp
206 management).

207 *Stopping criteria for an individual study dinner session:* A Study Dinner Session will be stopped
208 for an individual participant for any of the following:

209

- Ketones >1.5 mmol
- Known site failure

CLINICAL PROTOCOL

211 • Two separate hypoglycemia events where the blood glucose falls below 50 mg/dL
212 • The behavior of the participant is such that there is concern about his/her ability to
213 continue to adhere to the protocol
214 • At the discretion of the study physician.

215 **1.4 Study Device Download**

216 Before discharge from the hotel, all study devices will be turned in to study staff for device
217 download and the participants will be placed on usual diabetes management.

218 **1.5 Study System Issues**

219 If the CGM signal becomes unavailable for more than 20 minutes consecutively, closed loop will
220 not operate to automatically adjust insulin. If the CGM is not connected, the system will revert
221 to usual function of the pump and deliver insulin with the insulin dosing parameters programmed
222 in the system for that individual. Resumption of closed-Loop will occur automatically once CGM
223 signal is available again.

224 If the study system is unable to maintain pump connectivity, the pump will automatically revert
225 to pre-programmed basal insulin delivery after 30minutes without any need for instruction from
226 the user.

227 **1.6 Purpose/Objectives of Clinical Study**

228 **1.6.1 Study Participants**

229 Enrollment in the Pilot Study will proceed with the goal of completing 3 participants. Up to 6
230 participants may sign the consent/assent forms.

231 Enrollment in the Main Study will proceed with the goal of completing approximately 20

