608 The study physician will suggest appropriate treatment If CGM is <70 mg/dL or >250 mg/dL, or
609 ketone test is >0.6 mmol/L. The study team may request fingersticks as needed. The study
610 subject may continue participation in the trial once CGM is between 70-250 mg /dL and ketone
611 concentration is ≤ 0.6 mmol/L.

CLINICAL PROTOCOL

612 If CGM is >250 for more than 3 hours or >400 mg/dL at any time, study physician will be notified
613 and ketones will be checked. If ketone concentration is >0.6 mmol/L, the study team will check
614 the insulin pump infusion site and correction insulin will be administered per study physician
615 judgement via the subject's insulin pump. The study team will monitor CGM changes and ketones
616 will be checked every 60 minutes until ketone concentration is ≤0.6 mmol/L. If ketone
617 concentration is ≥3.0 mmol/L, the study physician will recommend the appropriate medical
618 treatment.

619 If CGM <60 mg/dL at any time, subjects will be given approximately 8-16 grams of fast-acting
620 rescue carbohydrates. Study team will monitor CGM rise and will consider treating again if CGM
621 <80 mg/dL after approximately 20 minutes. Hypoglycemic treatments can occur at any time per
622 study physician request.

623 **7.6 Study Meals**

624 Study Dinner Sessions start approximately 3-4 hours before the participant eats dinner and will
625 continue for approximately 12 hours after the dinner. Participants will eat a structured dinner at
626 approximately 6-7 pm during the admission. The order of the AP system tested (RocketAP vs.
627 Control-IQ) is determined randomly. The order of carbohydrate (CHO) announcement will be the
628 same in both cases (Table 1).

629

- Study Dinner Session #1 and #3: Normal CHO announcement
- Study Dinner Session #2 and #4: No announced CHO (Meal Control Module)

631 Blood glucose levels will be followed via continuous glucose monitor with the goal of maintaining
632 a blood glucose range 70-180 mg/dL during the 6 hours following start of the meal. The closed
633 loop session run between 3pm – 6 am and will be discontinued prior to time of discharge.

634 Breakfast and lunch will be announced into each system during the hotel admissions.

635 **7.7 Admission Activities**

636 Participants will be free to engage in low-intensity activity (i.e. walking, kicking soccer ball) during
637 the hotel admission. If COVID precaution milestones are met (all participants and on-site study

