1225 power calculation. (The pilot study for this proposal will assess ease of system use in up to 3
1226 individuals prior to the beginning of the main study.)

1227 **13.3 Outcome Measures**

1228 **13.3.1 Primary Efficacy Endpoint**

1229 The study design allows for multiple comparisons of blood glucose control during the Study
1230 Dinner Sessions, with for the primary comparison of interest being between the no carbohydrate
1231 announcement on the RocketAP (running the Meal Probability Detector and the Meal Control
1232 Module algorithms) compared to no carbohydrate announcement on the Control-IQ system. Our
1233 primary endpoint is time-in-range 70-180 mg/dL for the 6-hour period after dinner. Additional
1234 comparisons are made between the RocketAP system without vs. with normal carbohydrate
1235 announcement (which determines efficacy vs. premeal bolus), as well as the Control-IQ system
1236 without vs. with carbohydrate announcement (which determines risk of missed carbohydrate
1237 announcement in standard of care system).

1238 **13.3.2 Secondary Outcomes**

1239 For study period beginning after dinner and for 6h thereafter:

- 1240 • Number of hypoglycemia events
- 1241 • Time <70 mg/dL
- 1242 • Time >180 mg/dL

CLINICAL PROTOCOL

1243 • Time >250 mg/dL

1244 • Units of insulin injected

1245 • Area under the curve when accounting for starting BG

1246 For study period beginning of dinner until 12 hours later:

1247 • Time in range 70-180 mg/dL

1248 • Number of hypoglycemia events

1249 • Time <70 mg/dL

1250 • Time >180 mg/dL

1251 • Time >250 mg/dL

1252 • Units of insulin injected

1253 • Area under the curve when accounting for starting BG

1254 We will also assess both safety and efficacy of the RocketAP in adolescents by assessing outcomes
1255 outside of the Study Dinner Sessions:

1256 • Time in range 70-180 mg/dL

1257 • Number of hypoglycemia events

1258 • Time <70 mg/dL

1259 • Time >180 mg/dL

1260 • Time >250 mg/dL

1261 • Units of insulin injected

1262 **13.4 Safety Analyses**

1263 We will assess for the system's functionality, including the ability of the system to run its code
1264 without error (delivering insulin safely, as planned), as well as its ability to avoid low BG <70
1265 mg/dL.

CLINICAL PROTOCOL

1266 **13.5 Baseline Descriptive Statistics**

1267 Baseline demographic and clinical characteristics of the cohort of all randomized participants will

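### Sections 1.3.4, 1.3.5 and 7.6 conflict on when closed loop runs, so it is unclear how much of the outside-session outcomes in 13.3.2 is controller time

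*Combined protocol and SAP*

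**What the plan says.** The protocol describes main-study loop time in three places.

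- **Section 1.3.4:** "Participants will have their blood sugar managed through this system during the entirety of the" time at the hotel. This is the whole admission.
- **Section 1.3.5:** "The UVa AP systems will be initiated upon arrival to the hotel the afternoon/evening before the" first dinner session. At the end of the second session participants go to home insulin management. Meals other than the study dinners are described as taken on the artificial pancreas system, with normal announcement.
- **Section 7.6:** the closed "loop session run between 3pm – 6 am and will be discontinued prior to time of discharge". The next line adds: "Breakfast and lunch will be announced into each system during the hotel admissions".

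Section 7.6 separately defines a Study Dinner Session as running from about 3–4 h before dinner to about 12 h after it, with dinner at about 6–7 pm. Section 7.8 puts discharge at about 8 am. In the pilot study, section 6.6 continues closed loop outside the dinner session until discharge.

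Section 13.3.2 lists seven outcomes under "For study period beginning of dinner until 12 hours later" and six more for time outside the dinner sessions, introduced by "We will also assess both safety and efficacy of the RocketAP in adolescents by assessing outcomes" there. Neither list says how time off closed loop is handled. Section 13.6 plans to tabulate time in different operational modes but does not link this to the outcomes in 13.3.2.

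**The concern.** The outside-session outcomes include time below 70 mg/dL and the number of hypoglycemia events, and the protocol offers them as evidence on RocketAP's safety and efficacy. They can serve that purpose only if the assigned controller is running during the hours counted. Under 1.3.4 it runs throughout. Under 1.3.5 it runs until the second session ends. Under a literal 7.6 it is off from 6 am to 3 pm each day, which covers the usual breakfast and lunch hours and is most of the time outside the sessions. Staff could follow any one of these sections and still comply with the protocol, and the same outcome would measure something different each time.

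**Working it through.** The plan gives no statistical figure to reproduce here, so the check is clock arithmetic.

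**Inputs from the protocol.** Dinner 6–7 pm, session from 3–4 h before dinner to 12 h after, and closed-loop clock 3 pm to 6 am (7.6). Discharge about 8 am (7.8). Stay about 64 h (Protocol Summary). Study dinners on days 2 and 3 of the first admission (1.3.5).

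**Assumptions.** Arrival at 4 pm on day 1, which makes 64 h to 8 am on day 4. The 3 pm to 6 am clock also applies on the first night, because 1.3.5 starts the system on arrival.

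**Step 1: the 7.6 window.** 3 pm to 6 am is 15 h. A 6 pm dinner with a 3 h lead gives a session of exactly 3 pm to 6 am. A 7 pm dinner ends its session at 7 am, after the stated loop end.

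**Step 2: total time off the loop on the literal reading.** 6 am–3 pm on days 2 and 3, plus 6–8 am on day 4: 9 + 9 + 2 = 20 h. Time on the loop: 14 + 15 + 15 = 44 h, and 44 + 20 = 64 h.

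**Step 3: outside-session time.** Outside-session hours = 64 − 2 × (lead + 12). Off-loop hours outside sessions = 20 − (off-loop hours inside the two sessions).

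| Dinner | Lead | Session | Outside session (h) | Off loop, outside session (h) | Share |
|---|---|---|---|---|---|
| 6 pm | 3 h | 3 pm–6 am | 64 − 30 = 34 | 20 − 0 = 20 | 59% |
| 6 pm | 4 h | 2 pm–6 am | 64 − 32 = 32 | 20 − 2 = 18 | 56% |
| 6:30 pm | 3 h | 3:30 pm–6:30 am | 34 | 20 − 1 = 19 | 56% |
| 6:30 pm | 4 h | 2:30 pm–6:30 am | 32 | 20 − 2 = 18 | 56% |
| 7 pm | 3 h | 4 pm–7 am | 34 | 20 − 2 = 18 | 53% |
| 7 pm | 4 h | 3 pm–7 am | 32 | 20 − 2 = 18 | 56% |

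**Step 4: sensitivity to the stay.** Arrival at 3 pm adds one on-loop hour, and the lowest share becomes 18/35 = 51%. Arrival at 6 pm removes two, and the highest becomes 20/32 = 62.5%. Chapter 7 allows up to 90 h. A 90 h stay ending at 8 am starts at 2 pm and has 1 + 27 + 2 = 30 h off the loop. The share is then 30/60 = 50% (6 pm dinner, 3 h lead) down to 28/60 = 47% (7 pm dinner, 3 h lead).

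**Step 5: the other two accounts.** Under 1.3.4, no outside-session hours are off the controller. Under 1.3.5, only the time from the end of the second session (6–7 am) to 8 am is off: 1–2 h, or about 3–6% (1/34 to 2/32).

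**Step 6: dinner windows on the literal reading.** The 12-hour window ends at 6–7 am, so it loses 0 h (6 pm dinner), 0.5 h (6:30 pm, 0.5/12 = 4.2%) or 1 h (7 pm, 1/12 = 8.3%). The 6-hour primary window ends between midnight and 1 am and loses 0 h.

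**The case against.** The strongest reply is that 7.6 never says the loop is off in the daytime. Its clock hours match the dinner session for a 6 pm dinner with a 3 h lead, so the sentence may only be giving that session's times. The next line announces breakfast and lunch into each system, 1.3.5 places the other meals on the system, and the pilot text keeps closed loop running until discharge. On that view the mismatch with 1.3.4 shrinks to the last 1–2 h before discharge.

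This reading is plausible, and a reader should not infer that 7.6 restricts closed loop to those hours. It does not settle the matter, for three reasons. Section 7.6 has already defined the dinner session, and it then names a closed-loop session and says that it is discontinued. A 6 am end does not fit a 7 pm dinner. Announcing a meal to a system does not prove that automation is active: 1.5 and 5.3.2 describe reversion to ordinary pump function and an open-loop mode. Even on the benign reading, 1.3.5 still conflicts with 1.3.4 after the second session.

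Two larger inferences are tempting and are not supported.

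- **All thirteen 12-hour and outside-session outcomes are compromised.** The seven 12-hour outcomes lose at most about 1 h, on times the protocol calls approximate, with the same nominal clock for both systems. The outside-session outcomes are also framed as an assessment of RocketAP, with no between-system contrast specified, so a diluted treatment difference is not the main issue.
- **Controller exposure before the unannounced day-3 dinner falls from about two days to 3–4 h.** Only the uninterrupted run shortens. On the literal reading the loop has already run 14 h on the first night and 15 h around the day-2 dinner.

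**Conclusion.** The conflict among 1.3.4, 1.3.5 and 7.6 is real and unresolved, and 13.3.2 has no rule that would absorb it. Its weight falls on the six outside-session outcomes. On the literal 7.6 reading and a 64 h stay from 4 pm on day 1, 53–59% of the time behind them is off the controller. The figure is 51–62.5% for arrivals between 3 and 6 pm, and about half if the stay reaches 90 h. On the 1.3.4 or 1.3.5 reading it is 0% or about 3–6%. The protocol does not show which applies. The 12-hour outcomes are touched only at the margin, and the primary endpoint is unaffected on any reading. For a feasibility-sized study this is a secondary-outcome problem, but it bears on a stated safety assessment and should be corrected.

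**What to change.** Reconcile 1.3.4, 1.3.5 and 7.6 so that they give one account of when closed loop runs, including the daytime hours and the time between the second session and discharge. Which schedule is intended is for the investigators to state.

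In 13.3.2:

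- Define the outside-session and 12-hour windows by scheduled closed-loop hours, with the same clock limits for both systems.
- Keep unplanned loop outages inside those windows, such as CGM loss or lost pump connectivity (1.5) and the loop-off period after insulin given outside the pump (5.3.2). Restricting the outcomes to time when the controller was actually active would select on device behaviour after randomization and drop hours that a safety analysis should count.
- Report controller-active hours per system beside each outcome, from the operational-mode data planned in 13.6.

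The existing 13.6 exclusion of nights with site failure or CGM malfunction is a separate rule that this change leaves alone. The cost is a few sentences in four sections and the IRB review that 15.2 requires for any amendment. The analysis change needs no new data collection.

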232 participants. Up to 30 participants may sign the Main Study consent/assent forms.

233 **1.6.2 Clinical Sites**

234 The study will be performed at the University of Virginia, with screening procedures taking place
235 at the Clinical Research Unit or at a local hotel/rental house.

CLINICAL PROTOCOL

236 **Chapter 2 Study Devices**

237 **2.1 Insulin Pump**

238 The study systems will utilize the Tandem t:ap research pump connected to the UVa DiAs system
239 run on a dedicated external smart phone, running either the RocketAP control algorithm or the
240 Control-IQ control algorithm (in random order).

241 **2.2 Continuous Glucose Monitor**

242 The study CGM will include Dexcom G6 transmitter and sensors. The CGM sensor is viable for 10
243 days.

244 **2.3 Blood Glucose Meter and Strips**

245 Blood glucose levels will be measured using the Accu-Chek Guide blood glucose meter
246 (glucometer). The CGM device will be calibrated, if needed, using the study glucometer and strips
247 in accordance with the manufacturer's labeling.

248 **2.4 Ketone Meter and Strips**

249 Blood ketone levels will be measured using the Abbott Precision Xtra meters and strips in
250 accordance with the manufacturer's labeling. The blood glucose meter component of the
251 Precision Xtra Device will not be used. The ketone meter will be available for staff use during the
252 study admissions.

253 **2.5 Study Devices Accountability Procedures**

254 Device serial numbers will be recorded and use of equipment will be tracked.

CLINICAL PROTOCOL

255 **Chapter 3 Study Screening**

256 **3.1 Participant Recruitment and Enrollment**

257 Pilot Study: Enrollment goal in the Pilot Study will be to complete 1 participant. Up to 4
258 participants may sign consent/assent forms.

259 Main Study: Enrollment in the study will proceed with the goal of completing up to 20
260 participants. Participants will initially be randomized for the order of their 3 experimental meals
261 use during the study. Up to 30 participants may sign the consent/assent forms.

262 **3.2 Informed Consent and Authorization Procedures**

263 Before consent has been obtained, participants will be asked inclusion/exclusion criteria
264 questions during pre-screening to determine study eligibility. Before completing any procedures
265 or collecting any data that are not part of usual care, written informed consent (and assent, when

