638 personnel are found to be COVID-negative on second study COVID test performed at entrance to
639 the “bubble,” see Section 10.3), limited activities with safe distancing and mask use may occur as
640 described in Section 10.3. Participants will enjoy quiet activities in the evening.

CLINICAL PROTOCOL

641 **7.8 Admission Discharge**

642 Discharge will be at approximately 8 a.m. If the CGM values are above 300 mg/dL and ketone
643 values are >0.6 mmol/L, the study team will check the insulin pump infusion site and correction
644 insulin will be administered per study physician judgement via the subject's insulin pump.

645 Participants will be asked to continue monitoring ketone levels for 24-48 hours after the hotel
646 admission if ketones were present at time of discharge. Urine ketone supplies may be provided
647 for this testing.

648 **7.9 Post Admission Questionnaire**

649 Participants will complete questionnaire(s) at the completion of each admission. Questionnaires
650 are described in section 9.2.

651 **7.10 Post Admission Check-In Visit**

652 Approximately 24-48 hours after the hotel admission, the study team will contact the participant
653 via phone/email/text to assess adverse events, adverse device effects, and device issues Medical
654 Monitor Review

655 **7.11 Medical Monitor Review**

656 At the conclusion of the Pilot Study, the medical monitor will review the data as referenced in
657 section 8.3.

CLINICAL PROTOCOL

658 **Chapter 8 Medical Monitor Review**

659 **8.1 Medical Monitor Study Safety Data Review**

660 The Medical Monitor will be provided all adverse event data from the Pilot Study for review prior
661 to the main study. The Medical Monitor will review data related to individual stopping criteria
662 as detailed in the study protocol.

663 **8.2 Medical Monitor Decisions**

664 After review, the Medical Monitor can recommend that the current study continue without
665 modification, continue with specified modifications, discontinue one or more arms of the study,
666 or halt or modify the study until more information is available.

667 The Medical Monitor may recommend modifications to individual stopping rules if additional
668 safety concerns arise during from their continuing reviews of the study data.

669 The hotel admission will not be repeated unless required by the Medical Monitor.

670 **8.3 Medical Monitor Main Study Safety Data Review**

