11.2 Reportable Events

For this protocol, a reportable adverse event includes any untoward medical occurrence that meets one of the following criteria:

- A serious adverse event as defined in section 11.2
- An Adverse Device Effect as defined in section 11.1.4, unless excluded from reporting in section 11.7
- An Adverse Event as defined in section 11.1.1 occurring in association with a study procedure
- An AE as defined in section 11.1.1 which leads to discontinuation of a study device for 2 or more hours
- Hypoglycemia meeting the definition of severe hypoglycemia as defined in section 11.2.1
- Diabetic ketoacidosis (DKA) as defined in section 11.2.2 or in the absence of DKA, a hyperglycemic or ketosis event meeting the criteria defined below

Hypoglycemia and hyperglycemia not meeting the criteria below will not be recorded as adverse events unless associated with an Adverse Device Effect. Skin reactions from sensor placement are only reportable if severe and/or required treatment.

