11.2.2 Hyperglycemia Events/Diabetes Ketoacidosis

1024 Hyperglycemia not associated with an Adverse Device Effect is only reportable as an adverse
1025 event when one of the following four criteria is met:

1027 • the event involved DKA, as defined by the Diabetes Control and Complications Trial
1028 (DCCT) and described below evaluation or treatment was obtained at a health care
1029 provider facility for an acute event involving hyperglycemia or ketosis

1030 • blood ketone level ≥ 1.5 mmol/L and communication occurred with a health care provider
1031 at the time of the event

1032 • blood ketone level ≥ 3.0 mmol/L, even if there was no communication with a health care
1033 provider

1034 Hyperglycemic events are classified as DKA if the following are present:

1035 • Symptoms such as polyuria, polydipsia, nausea, or vomiting

1036 • blood ketones ≥ 1.5 mmol/L or large/moderate urine ketones

1037 • Treatment provided in a health care facility

1038 All reportable Adverse Events—whether volunteered by the participant, discovered by study
1039 personnel during questioning, or detected through physical examination, laboratory test, or
1040 other means—will be reported on an adverse event form online. Each adverse event form is
1041 reviewed by the Medical Monitor to verify the coding and the reporting that is required.

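### The two ketone-level reporting criteria are blood values only, while the home monitoring after discharge names only urine tests, so some home-managed ketosis would not count as an adverse event

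*Combined protocol and SAP*

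**What the plan says.** Sections 6.8 (pilot) and 7.8 (main study) carry the same instruction. A participant who has ketones at discharge goes on checking them for 24-48 hours: "admission if ketones were present at time of discharge. Urine ketone supplies may be provided". No other home supply is mentioned. Section 2.4, on the blood ketone meter, says "The ketone meter will be available for staff use during the" study admissions.

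Section 11.2.2 makes hyperglycemia outside an Adverse Device Effect (ADE) a reportable "event when one of the following four criteria is met". The criteria are DKA; evaluation or treatment at a health care "provider facility for an acute event involving hyperglycemia or ketosis"; a blood ketone level of at least 1.5 "mmol/L and communication occurred with a health care provider"; and a blood ketone level of at least 3.0 mmol/L with or without such communication. The first two are run together in one bullet, but the stated count of four shows that they are separate. The DKA definition that follows lists, as its ketone element, blood ketones of at least 1.5 "mmol/L or large/moderate urine ketones", together with symptoms and treatment in a facility.

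Section 11.2 sets the consequence of missing the criteria: "Hypoglycemia and hyperglycemia not meeting the criteria below will not be recorded as adverse events unless associated with an Adverse Device Effect".

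Sections 6.9 and 7.10 schedule a remote contact about 24-48 hours after each admission to ask about adverse events, device effects and device issues. They do not mention ketone results.

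**The concern.** The plan asks for a safety measurement and then offers a test whose result its own ketone-level criteria cannot use. The same section shows that urine results were considered, since the DKA definition accepts them.

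The timing gives this some weight. In the main study the dinner without carbohydrate announcement is the second study dinner of each admission (Table 1, section 7.6), so discharge follows the next morning. Section 1.3.5 anticipates more significant hyperglycemia with these dinners, and 10.1.5 calls hyperglycemia likely. Neither the secondary outcomes (13.3.2) nor the safety analyses (13.4) include a ketone measure, so adverse event reporting is the only stated route by which ketosis after discharge enters the safety results. The Medical Monitor reviews adverse event forms (11.2.2) and receives the pilot's adverse event data before the main study starts (8.1).

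At stake is an under-count of home-managed ketosis in the safety record. The primary endpoint is not affected.

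**Working it through.** The plan gives no figure to reproduce and no power calculation is involved. The check sets the sections side by side and asks which reporting routes a urine-only result after discharge can satisfy.

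**Inputs**
- Home test named: urine, optional (6.8, 7.8).
- Blood ketone meter: described for staff during admissions; no home provision stated (2.4).
- Reporting criteria: four, any one sufficient (11.2.2).
- Route outside the criteria: association with an ADE (11.2, with the definition in 11.1.4).

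**Routes for ketosis at home after discharge**

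| Route | What it needs | Open to a participant who has only a urine result and is managed at home? |
|---|---|---|
| DKA | Symptoms, ketones (blood or urine), treatment in a facility | No, because there is no facility treatment |
| Facility evaluation or treatment | A facility contact; no ketone value | No, for the same reason |
| Blood ketones ≥1.5 mmol/L | A blood value and provider communication at the time | No, because there is no blood value |
| Blood ketones ≥3.0 mmol/L | A blood value | No, because there is no blood value |
| Association with an ADE | A judgment that the device may have caused or contributed to the event | Yes, if so judged |

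The type of test by itself closes two of the four criteria. The other two close only because the event is managed at home. For ketosis short of DKA there are four routes: facility care, two blood thresholds and the ADE route. A urine-only result is shut out of two of these four. It is shut out of all four only when there is also no facility evaluation or treatment and no ADE judgment.

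**Other entries in 11.2.** The exclusion sentence speaks of hypoglycemia and hyperglycemia. Ketosis without DKA enters through the last item of the list, which points to the same criteria. The item for events associated with a study procedure might be argued to cover ketosis after an unannounced dinner, but the same section confines hyperglycemia to the listed criteria or an ADE, so its application is unclear.

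**Timing of the contact.** Monitoring lasts 24-48 hours and the contact falls at about 24-48 hours. A contact at 24 hours can precede the end of a 48-hour monitoring period by 48 − 24 = 24 hours. Later in the window the two coincide.

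**Upper bound.** Main-study discharges: up to 20 participants × 2 admissions = 40. Pilot discharges: up to 3. The instruction applies only where ketones are present at discharge, and the gap only to a subset of those. The documents give no rate for either.

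**The case against.** A reader might infer that the reporting rules rest on blood values alone, so that ketosis at home after an unannounced dinner can never be reported and is lost. The documents do not support that.

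- Facility evaluation or treatment for ketosis is a criterion of its own and needs no ketone value.
- The ADE definition in 11.1.4 is broad. Ketosis plausibly linked to either system can be reported at any ketone level.
- Section 11.2 says that such events are not recorded as adverse events. It does not say that the results are unrecorded altogether, and 6.9/7.10 schedule a contact at which they may be heard of.
- Urine supplies are optional and no home method is prescribed. A participant's own blood meter is not excluded.

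The importance of the late period can also be questioned. The response to the last dinner is watched in the hotel from about 6-7 pm to discharge at about 8 am, some 13-14 hours. Ketones are checked there under the conditions in 6.5 and 7.5 with a blood meter, so the 11.2.2 thresholds apply to those values. Section 7.6 ends closed loop before discharge, and the participant returns to usual management, so later ketosis is partly a product of home pump use. The Medical Monitor's pilot review also covers data on individual stopping criteria (8.1), not adverse events alone.

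Finally, urine ketones appear in 11.2.2 only beside symptoms and facility treatment. That is not a stand-alone equivalence to 1.5 mmol/L.

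All of this narrows the point without removing it. The facility route misses events managed at home. The ADE route asks for a causal judgment about an event that arises after the study devices have been handed in (1.4). The contact collects adverse events, and hearing of a urine result there does not make it meet a blood criterion.

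**Conclusion.** The concern holds in a limited form. Ketosis after discharge that is found only by urine test, managed at home without facility evaluation or treatment, and not judged to be associated with an ADE meets none of the 11.2.2 criteria and would not be recorded as an adverse event under 11.2. The conclusion assumes that urine supplies are in fact what is used and that the study-procedure item of 11.2 does not override the restriction on hyperglycemia.

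The size cannot be estimated. The 40 main-study and 3 pilot discharges bound how often monitoring could be requested; they do not count missed events. The unannounced dinner comes last under both systems in the main study, so the gap applies to RocketAP and Control-IQ alike. The material shows an under-count and gives no basis for claiming a bias between them. It does not show that post-discharge ketosis in general escapes reporting.

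**What to change.** Reconcile 6.8/7.8 with 11.2.2 so that the reporting criterion for results obtained after discharge can be applied to the test offered. One way is to extend the urine category already in the DKA definition to the reporting of post-discharge events. The added clause should state whether the provider-communication condition applies to such results and, if so, whether the check-in contact satisfies it. Otherwise a participant who tests at home and calls nobody would still fall outside the rule.

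In 6.9 and 7.10, add that the home ketone results are collected and recorded at a contact made at or after the end of the monitoring period.

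The cost is one clause in 11.2.2, one line in each check-in section and a few more adverse event forms. Urine grades are a coarser measure than blood values, so these events should be identifiable as urine-based in the listings. The change concerns event reporting only; no change to treatment, home testing method or clinical thresholds is proposed.
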